We hypothesize that sites randomized to REP + CONNECT will have higher penetration (for STRIDE that is the proportion of eligible patients with \geq 1 documented walk during hospitalization, higher total daily minutes of activity and distance walked, and higher proportion of eligible patients who report their providers wanted them to walk while they were in the hospital; and for iHI-FIVES that is the proportion of eligible caregivers reached by iHI-FIVES in a 6-month interval and the proportion of providers involved in caregiver support who refer caregivers to participate in iHI-FIVES in a 6-month interval) and **fidelity** (higher proportion of STRIDE participants with \geq one documented supervised walk, and with \geq 10 minutes of daily walking); for iHI-FIVES proportion of sites that delivered at least two rounds of iHI-FIVES trainings in a 6-month interval during post-implementation and the proportion of training rounds from the total number offered in which the full iHI-FIVES core curriculum topics were covered). For Aim 1, outcomes are defined in the post-implementation period only and the primary analyses will be for the outcomes in the first post-implementation 3-month period so that analysis will not be confounded with time since implementation. For the dichotomous outcomes, we will use logistic regression models⁵⁵⁻⁵⁷ where the main predictor of interest will be REP vs. REP + CONNECT adjusting for clustering of VAMC with either a random effect or by conditioning. For continuous outcomes, we will use linear mixed regression models.⁵⁸ Adjustments for patient characteristics and a random effect for hospital ward may also be added. In hospitals that have multiple post-implementation 3-month measurement times, we will examine how fidelity and penetration outcomes change over time using descriptive methods (e.g. plots, descriptive statistics, subgroups).

In addition to testing the above quantitative hypotheses, we will use semi-structured interviews with providers to elicit their experience with implementation process and evaluation of outcomes. Specifically, we will ask providers questions about team processes, for example, *How do team members communicate with each other*

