Quantitative analyses for Aim 2 will be conducted at the level of the patient, utilizing all available data to evaluate STRIDE effectiveness on defined dichotomous, count and continuous outcomes. The overall anticipated sample size of eligible STRIDE patients during pre- and post-implementation periods is 2000. The anticipated maximum sample is 16,000. Only a subset of STRIDE eligible patients will receive survey measures in both the pre- and post-implementation periods. We will use random effect linear (continuous outcomes), negative binomial (count outcomes), or logistic (dichotomous outcomes) models appropriate for the stepped-wedge design which account for the correlation of patients within the same VAMC.^{34,60} For example with a continuous outcome, I VAMCs, T time points, N individuals per VAMC per time interval, the model is: $Y_{ijk} = \mu + \alpha_i + \beta_j + X_{ij}\theta + e_{ijk}$, where α_i is the random effect for the ith VAMC, β_j is a fixed effect that captures time trends, and X_{ij} is an indicator of the intervention mode for the ith hospital at time j (=0 prior to intervention and =1 post intervention), and θ is the measure of the effect of the intervention. Adjustments for patient characteristics and a random effect for hospital ward may also be added.

Qualitative data will be collected via 30-45 minute semi-structured telephone interviews with a sample of patients in STRIDE. Interviews will be audio recorded. We will ask patients about whether they found STRIDE to be helpful for them and in what ways and if they have suggestions for improvement. We will analyze data using conventional content analysis, in which we will transcribe interviews and then code text with descriptive labels that are developed as we read through transcripts. Data will be coded by a team process as described in Aim 1. Findings from Aims 1 and 2 will be supplemented by **budget impact analyses**

Aim 2b: To examine the **impact** of iHI-FIVES on key patient and caregiver outcomes.

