As described for Aim 1, Aim 3 outcomes are defined in the first post-implementation 3-month period so that analyses will not be confounded with time since implementation. To examine the relationship between team function and dichotomous implementation outcomes, we will use logistic regression models⁵⁷ where the main predictors of interest will be the baseline TDM[©] scores (e.g., overall, and team dimensions such as cohesion and role clarity) adjusting for clustering of VAMC with either a random effect or by conditioning.^{55,56} Other responses from the provider survey instrument may collectively reflect other dimensions of team function. Using exploratory factor and cluster analysis methods, the implementation core will determine the appropriateness (i.e., with our operational partners) and reliability of constructing other composite measures of team function that will be incorporated in quantitative analysis to examine teams' mediating/moderating effects on implementation outcomes. For continuous outcomes, we will use linear mixed regression models.⁵⁸ In VAMCs that have multiple postimplementation 3-month measurement times, we will examine how fidelity and penetration outcomes change over time by TDM[©] scoreteam function using descriptive methods (e.g. plots, descriptive statistics, subgroups). Adjustments for covariates and a random effect for VAMC ward may also be added. If scores of team function are associated with implementation outcomes, we will explore whether they differentially affect implementation outcomes by patient and facility characteristics. If we find in Aim 1 that the implementation strategy REP + CON-NECT improves implementation outcomes compared to REP alone, we will examine whether team function mediates or moderates this effect following methods of MacKinnon⁵² and Kraemer.^{61,62} These quantitative findings from Aim 3 will be complemented by additional analyses of context sensitivity as described earlier.

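### The Aim 2a model gives STRIDE one constant effect over all post-implementation quarters; if benefit builds up after rollout, the estimate falls below the average effect, and no planned analysis would show it

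*Combined protocol and SAP*

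**What the plan says.** Under Analyses, Aim 2a, patient outcomes are modelled "utilizing all available data to evaluate STRIDE effectiveness". The model has a random site effect, and βj, which "is a fixed effect that captures time trends". The treatment variable is an "indicator of the intervention mode for the ith hospital at time j (=0 prior to intervention and =1 post intervention"), and a single θ "is the measure of the effect of the intervention". The only optional additions are patient characteristics and a random effect for ward.

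Time since implementation is handled elsewhere. The primary Aim 1 analysis uses only the first post-implementation quarter, "so that analysis will not be confounded with time since implementation". Under Aim 3, likewise, "Aim 3 outcomes are defined in the first post-implementation 3-month period". For sites with several post quarters, Aim 1 adds: "we will examine how fidelity and penetration outcomes change over time using descriptive methods". No such step is given for discharge to a skilled nursing facility (the primary patient outcome) or length of stay (the primary service outcome).

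The STRIDE Clinical Program Procedures and Figure 4 describe four steps of two sites, with a 3-month rollout period at each site between control and post-implementation time.

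**The concern.** Sites that start early contribute up to four post quarters and sites that start late only one, yet all share one θ. If the effect changes with time since implementation, the constant-effect estimator does not return its average. The later quarters of early sites serve as comparators for sites that have just switched, and the period effects absorb part of any growth.

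There is a plausible route to growth. Aim 2a analyses eligible patients, and penetration is the share of eligible patients with any documented walking. If penetration rises from quarter to quarter, an effect measured over all eligible patients could rise with it. This is an inference from the outcome definitions; the plan does not state it.

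At stake is how a small or null θ would be read. The results feed the budget impact analyses and the dissemination of STRIDE. A larger sample narrows the interval but does not remove the bias.

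**Working it through.** **Inputs.** From Sample size estimate: 8 sites, five 3-month periods, 50 patients per site-period (2,000 in all), maximum 16,000 (16,000/40 = 400 per site-quarter), base rate 20%, a 10% drop (read as 20% to 10%), ICC 0.02 to 0.6, alpha 0.05 (taken as two-sided). From Figure 4: four steps of two sites over six quarters.

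Assumptions of this check:
- The rollout quarter is removed, and block 2's administrative-only quarters are included.
- Total variance is 0.15 × 0.85 = 0.1275.
- The ICC is 0.02 to 0.06, narrower than the plan's range; its upper value of 0.6 was run as well.
- The effect curves are assumed, because the documents give none.

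**Step 1: the plan's own power.** Hussey–Hughes variance, complete five-period design, 50 per cell, total variance 0.20 × 0.80 = 0.16, power = Φ(10/SE − 1.96). The SE is 3.07, 3.06 and 2.06 points at ICC 0.02, 0.1 and 0.6, giving 90%, 90% and more than 99%. The stated power of at least 80% reproduces, for a constant effect.

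**Step 2: cells in Figure 4.** After rollout, the four steps have 4, 3, 2 and 1 post quarters. With two sites each, exposure quarters 1 to 4 hold 8, 6, 4 and 2 treated cells (20). There are 2 × (1 + 2 + 3 + 4) = 20 control cells, so 40 in all.

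**Step 3: weights.** θ̂ is the treatment element of (D′V⁻¹D)⁻¹D′V⁻¹Y, where D holds the 0/1 indicator and the period effects and V is the random-intercept covariance. Summing its weights by exposure quarter gives E[θ̂] = Σ w_s δ_s, where δ_s is the effect in exposure quarter s and Σ w_s = 1. Over ICC 0.02 to 0.06 and 50 or 400 per cell:

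- w₁ = 1.13 to 1.24
- w₂ = 0.25
- w₃ = w₄ = −0.19 to −0.25

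**Step 4: expected estimates, as a fraction of full effect.** The treated-cell average is (8δ₁ + 6δ₂ + 4δ₃ + 2δ₄)/20.

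| Assumed effect, quarters 1–4 | Treated-cell average | E[θ̂] |
|---|---|---|
| 50/100/100/100% | 0.80 | 0.38 to 0.44 |
| 25/50/75/100% | 0.50 | 0.00 to 0.08 |
| 80/100/100/100% | 0.92 | 0.75 to 0.78 |
| 100/90/80/70% (waning) | 0.90 | 1.07 to 1.10 |

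Example, second row, 50 per cell and ICC 0.02: 0.25 × 1.127 + 0.50 × 0.25 − 0.75 × 0.188 − 1.00 × 0.188 = 0.08. At 400 per cell and ICC 0.02 it is 0.01, so more patients do not help. At ICC 0.6 the first two rows are 0.38 and 0.00.

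**Step 5: logistic check.** Expected counts with fixed site effects, and a linear build-up on the logit scale to the full 20%-to-10% effect (log odds ratio −0.811). The constant-effect estimate is −0.034, against −0.811 × 0.625 = −0.507 for the equally weighted average of the four exposure quarters: 7% of it.

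**Step 6: price of separate quarter effects.** SE of the average over post quarters 1 and 2, against the SE of θ̂ (40 cells, ICC 0.02 to 0.06):

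- 400 per cell: about 1.65 against 1.3 points.
- 50 per cell: 4.19 to 4.43 against 3.65 to 3.68 points. Power for 10 points is Φ(10/4.19 − 1.96) = 67% down to Φ(10/4.43 − 1.96) = 62%, against 78%.

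**The case against.** **The plan never predicts growth in patient benefit.** This stands. A reader might infer from Aims 1 and 3 that it expects the STRIDE effect to rise. Those passages take a precaution for implementation and team analyses, and propose to describe penetration and fidelity over time. They say nothing about the course of discharge or length of stay.

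**The rollout quarter is already a buffer.** This stands in part. STRIDE acts within one hospital stay, so growth after rollout needs rising delivery, and a build-up finished within rollout does no harm. But the exclusion of rollout-window patients is written only for the surveys, and nothing says delivery is stable afterwards.

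**A reader might infer that any programme needing a quarter or two to settle would be reported as ineffective.** That is too strong. For half then full, with a 10-point full effect and 400 per cell, the expected estimate is about 3.8 points with SE 1.3 and power about 82%: attenuated, but usually detected. At 50 per cell, power is about 20%. An estimate near zero needs a slower build-up, and only two of the eight sites reach a fourth post quarter.

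**A reader might also expect a sign reversal.** Without block 2's first two quarters (32 site-quarters) the first two curves give 0.17 to 0.34 and −0.24 to −0.03. That layout fits the surveys: 150/30 = 5 quarters per block 1 site, 90/30 = 3 per block 2 site, and 4 × 5 + 4 × 3 = 32. Discharge and length of stay come from administrative records, for which the plan points to all available data.

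**The model is introduced as an example for a continuous outcome.** True, but no other treatment term is offered for the logistic or negative binomial models.

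**Conclusion.** The concern holds as a conditional one. The Aim 2a model forces one effect on all post quarters and no planned analysis would reveal a departure. If the effect grows after rollout, θ̂ falls below the average effect, because quarters 3 and 4 carry negative weight. The size depends on a curve that the documents do not give: close to total loss for a steady four-quarter build-up, about half for a one-quarter lag at half effect, mild when 80% is present at once, none when build-up ends within rollout, and overestimation when the effect wanes. The figures rest on the random-intercept model, 40 site-quarters with the rollout quarter removed, and total variance 0.1275; the ICC makes little difference to the bias. The documents do not support saying that the effect will grow or that STRIDE will be wrongly found ineffective.

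**What to change.** Label: cheap improvement. Keep the constant-effect model as primary. Then:

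- Pre-specify a sensitivity analysis for discharge to a skilled nursing facility and length of stay in which the single indicator is replaced by separate effects for each quarter since implementation. Report each quarter's effect and one pre-named summary, the average over post quarters 1 and 2.
- Call that summary the early effect. Under a 25/50/75/100% build-up it targets (0.25 + 0.50)/2 = 0.375 of full effect, not the overall 0.50.
- Set no rule by which this analysis takes over when it differs, since that would let the data choose the headline result. State instead that a null constant-effect result will be interpreted alongside it.
- Confirm that block 2's administrative-only quarters enter these models. The STRIDE Clinical Program Procedures start block 2's pre-implementation period at time 6, while Figure 4's key and the Aim 2a data statement imply that the earlier quarters are used.

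The cost is a paragraph of analysis plan and one more model per outcome on data already collected, with a wider interval. Near 16,000 patients this matters little for a 10-point effect. At 2,000, power for the early effect is 62 to 67% against 78% for the constant-effect model in the same layout, and the plan should say so.

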To create the primary outcome, measures from administrative data and VA/CMS Repository data will be created that include patient ED days, inpatient days, post-acute facility days, and residential nursing home stays. These are all defined below, along with contextual utilization variables. We examine whether patients had a residential nursing home stay because we do not include those types of stays in our primary outcome and because patients who have transitioned to residential care of this type are no longer considered to be "independent" or living at home. As such, any days occurring in a visit of these types, will be censored and not included in the analysis as a day not at home. The outcome period is defined as from the mid-point of each 6-month block forward 6 months (e.g., the last day of month 3 in a block).

Emergency Department (ED) Days. We will count an emergency department encounter occurring on one day (two days, etc.) as one day (two days, etc.) not at home. For any ED visit that results in an inpatient admission on the same day as the ED visit, we will count the first day as being an ED day. Days thereafter that are spent in the inpatient setting, defined as there being a record of a hospital admission within one day of their ED visit, will be counted under the inpatient variable, described below.

Inpatient Days. We will use the admission date and the discharge date to calculate days spent in an inpatient stay. Inpatient hospice stays will be not included in the Inpatient Days count. Residential Psychiatric Inpatient Days will not be counted in the Inpatient Days count. See below for definitions of each of these. We will cross reference Inpatient Days against ED Days and Post-Acute Facility Days to prevent double counting.

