To address the impact of the iHI-FIVES program, we will use quantitative methods to examine the effect on patient outcomes. The overall anticipated number of eligible Veteran patients in the iHI-FIVES study will be 15,000-18,000 total patients. The analysis plan of our primary outcome is to examine days at home for the patient over a 6-month interval and will be defined as the total number of days not in the emergency department, nursing home, or inpatient ward. The start date for each patient, or the day of the automated data pull, will be "day 0" for all patients, and the maximum total possible number of days at home will be 180 for all patients. To make this outcome variable easier to deal with analytically, our first step will be to calculate each patients' days not at home by subtracting their number of days at home from 180, converting the "stack" of days at 180 to a "stack" at zero. For days not at home outcome, we anticipate, that it may have an excess of zeros and larger variance than what is to be expected from either a Poisson or Negative Binomial process. Common approaches for analyzing this type of data are the zero-inflated Poisson (ZIP) model and the zero-inflated negative binomial (ZINB) model¹¹⁶ or two-part models.^{117,118} Consequently, we will explore the distribution that best fits this outcome: Poisson, Negative Binomial, ZIP, ZINB, or a semi-continuous distribution such as a two-part gamma.¹¹⁹

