To address if caregivers who participate in iHI-FIVES have higher satisfaction with VA care, lower depressive symptoms, and lower burden, analysis will be conducted at the level of the patient or caregiver utilizing all available data to evaluate iHI-FIVES effectiveness versus control condition on defined count and continuous outcomes. The overall anticipated sample size of eligible caregivers in the iHI-FIVES study will be 320. We will use random effect linear (continuous outcomes), negative binomial (count outcomes), or logistic (dichotomous outcomes) models appropriate for the stepped-wedge design which account for the correlation of patients within the same VAMC.^{34,60} For example with a continuous outcome, I VAMCs, T time points, N individuals per VAMC per time interval, the model is: $Y_{ijk} = \mu + \alpha_i + \beta_j + X_{ij}\theta + e_{ijk}$, where α_i is the random effect for the ith VAMC, β_j is a fixed effect that captures time trends, and X_{ij} is an indicator of the intervention mode for the ith hospital at time j (=0 prior to intervention and =1 post intervention), and θ is the measure of the effect of the intervention. Adjustments for patient characteristics and a random effect for VAMC site may also be added.

Sensitivity analysis. In addition to the primary analysis of the primary and secondary outcomes described above, we will perform an "as treated" analysis focused on the outcomes of Veteran patients from caregivers in the post-implementation period exclusively. This will show us whether there is benefit conferred upon those caregivers/Veterans in the iHI-FIVES program compared to similar caregivers/Veterans not in the program. The treated caregivers will be all caregivers who meaningfully participated in the iHI-FIVES training (e.g., attended at least one class). The comparison caregivers will be selected from the full set of caregivers referred to iHI-FIVES using n:1 matching on key baseline covariates of the patient and caregiver. The rationale for matching on key Veteran baseline covariates is to ensure that we have similar Veteran acuity in both groups, because the training may be differentially effective for caregivers by level of Veteran disability. Candidate matching variables for the patient include:

- Patient age bands
- Patient Jen Frailty Index Score (0-10)
- Patient CAN scores (1 year inpatient use version)
- Dementia status based on ICD9 codes in the past 6 months
- Documentation of incontinence in the past 6 months

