Based on the sample size, we may use only a subset of these matching variables, and use exact and distancematched methods. Candidate matching variables for the caregiver will include: age, race, employment status, education, and caregiver relationship to the Veteran. We will use the same analysis techniques for the "as treated" analysis as described above. Or we may simply use regression adjustment if sample size is too low, from the candidate set of covariates described here.

To address the value of iHI-FIVES from the caregiver's perspective, qualitative data will be collected via 15-20-minute semi-structured telephone interviews with a sample of caregivers who participate in iHI-FIVES. Interviews will be audio recorded. We will ask patients about whether they found iHI-FIVES to be helpful for them and in what ways and if they have suggestions for improvement. We will analyze data using conventional content analysis, in which we will transcribe interviews and then code text with descriptive labels that are developed as we read through transcripts. Data will be coded by a team process as described in Aim 1. Findings from Aims 1 and 2 will be supplemented by **budget impact analyses**.

Aim 3: To determine the conditions under which STRIDE implementation is most successful.

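### The iHI-FIVES as-treated analysis does not tie the start of follow-up to class attendance, so it probably favours the programme by an amount the documents do not fix

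*Combined protocol and SAP*

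**What the plan says.** The as-treated comparison is set out under Analyses, Aim 2b, Sensitivity analysis, and uses post-implementation data only.

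- **Exposure:** "The treated caregivers will be all caregivers who meaningfully participated in the iHI-FIVES training (e.g., attended at least one class". No date limit relative to the start of follow-up is given.
- **Comparator:** "The comparison caregivers will be selected from the full set of caregivers referred to iHI-FIVES using n:1 matching on key baseline covariates". No index date is assigned to comparators.
- **Method:** the techniques already described for Aim 2b are reused, with regression adjustment as a fallback if numbers are small. No landmark or time-varying exposure is mentioned.

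The start of follow-up is defined twice. Aim 2b places day 0 for every patient at one event ("The start date for each patient, or the day of the automated data pull") and adds that "the maximum total possible number of days at home will be 180 for all patients". The section defining the primary outcome says instead: "The outcome period is defined as from the mid-point of each 6-month block forward 6 months".

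On class timing, the study timeline requires at least two rounds of training per 6-month period. The patient-sample section puts the pull at a uniform but unspecified point of each 3- or 6-month interval. No section dates a class relative to a pull.

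**The concern.** Attendance is an event, and a caregiver is less likely to attend if the Veteran has died or is in hospital or a facility when classes run. If follow-up starts before the class, the attenders' Veterans have been selected for being alive and mostly at home up to the class. Veterans with early bad outcomes move to the comparison group and take their days away from home with them. This is the usual immortal-time and selection problem. The matching variables (age band, frailty score, CAN score, dementia, incontinence, caregiver characteristics) describe the position at baseline and cannot balance events after it.

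The plan expects this analysis to show whether participants benefit. If the 320 in the caregiver enrolment section is read as the number of participating caregivers, they correspond to 320/18,000 = 1.8% to 320/15,000 = 2.1% of the Veterans in the primary analysis. Any effect among participants is heavily diluted there, so readers may lean on the as-treated result.

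**Working it through.** **1. The plan's own figure.** The documents give no figure for the as-treated comparison. The only related one is at least 80% power for the primary outcome with 400 Veterans (Sample size estimate).

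Inputs: 8 sites, 5 periods, mean 8 days, reduction 2 days, variance 8 (Poisson), CV 0.3 to 0.5. Two sites crossing over at each of four steps is assumed. Then n = 400/40 = 10 per site-period, σ² = 8/10 = 0.8 and τ² = (0.3 × 8)² = 5.76. The design sums are U = 20, W = 120 and V = 60.

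Hussey–Hughes: Var = Iσ²(σ² + Tτ²) / [(IU − W)σ² + (U² + ITU − TW − IV)τ²]

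- CV 0.3: 6.4 × 29.6 / (40 × 0.8 + 120 × 5.76) = 189.44/723.2 = 0.262. SE 0.512, power Φ(2/0.512 − 1.96) = 97.4%.
- CV 0.5 (τ² = 16): 6.4 × 80.8 / (32 + 1,920) = 0.265. Power 97.3%.

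The stated power holds. What remains is the 2-day planned effect, used below as a yardstick.

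**2. One channel by hand: deaths before the class.** Assumptions: constant hazard, 5% six-month mortality, class on day 60, 20% uptake, days after death counted as not at home, no training effect.

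- Hazard h = −ln(0.95)/180 = 0.000285 per day.
- Mean days lost, everyone: 180 − 0.05/h = 4.54.
- Mean days lost, attenders (alive at day 60): 120 − (1 − e^(−120h))/h = 2.03.
- Share attending: 0.2 × e^(−60h) = 0.197.
- Mean days lost, non-attenders: (4.54 − 0.197 × 2.03)/0.803 = 5.15.
- Spurious gain: 5.15 − 2.03 = 3.1 days (simulated: 3.09).

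The simulated values for classes on day 30 to day 90 are 0.7 to 1.7 days at 2% mortality and 3.5 to 8.4 at 10%.

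**3. Stays and deaths together.** Monte Carlo with no training effect. Institutional days were set at or near the plan's mean of 8. Attendance requires the Veteran to be alive and out of a facility on a class date. Days are counted from day 0. The contrast is unmatched. All inputs except the mean are assumptions.

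| Scenario | Apparent gain (days) |
|---|---|
| No deaths, one long stay per user, any of 4 classes qualifies | 1.0–2.8 |
| Same, one class date only | 1.6–3.8 |
| No deaths, repeated stays of mean 5–14 days, 4 classes | 0.0–0.9 |
| Same, one class date only | 0.5–2.1 |
| Any earlier stay blocks attendance | 1.9–7.2 |
| Days after death counted, 2% mortality, 4 classes | 1.8–3.4 |
| Same, 5% mortality | 3.1–6.1 |
| Same, 10% mortality | 4.9–10.3 |
| Days after death not subtracted | 0.6–1.7 |
| No deaths, 4 classes, comparators also alive and at home at a referral 21 days before class | about 0.8 |
| No deaths, half of classes before day 0 | 0.8–1.0 |

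In the 5% and 10% mortality rows the overall mean is about 12 and 17 days, because post-death days are added to the 8. The top of the range therefore does not fit a baseline mean of 8 if that figure already includes death.

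**4. With a common index date.** Both groups were required to be alive and at home on the class date, and days were counted from it (over 150 days in the simulation). The null difference was −0.10 to +0.08 days wherever this was run.

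**The case against.** The strongest reply is that the plan leaves the index date open and does not fix a wrong one.

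- No section says that classes follow the pull. With the block mid-point as the start, a round held in months 1 to 3 would come before day 0. This stands. It reduces the bias but does not remove it in the scenarios run.
- Day 0 appears in the paragraph on the primary outcome, and reusing techniques may mean only the models. Sites may also recruit caregivers outside the target list, whose Veterans may have no pull date. This too stands, and it means the start of follow-up must be stated for this analysis.
- The as-treated pool is telephoned before the first training, and the caregiver survey screen excludes Veterans currently in hospital, an institution or hospice. Comparators must have been referred. If comparators pass the same screen the bias shrinks, but the dates are still not aligned. If only attenders are screened near the class, it grows.
- Matching on CAN and frailty scores removes part of the gap. In an approximate rebuild, ideal matching on underlying risk cut it by 6–29% (any class qualifies), 11–48% (first date only) and 19–63% (a prior stay deters attendance). A gap remained.
- The outcome formula does not subtract days after death, although the outcome is described as being alive and at home. Nor does it count every facility day. It cannot be assumed that deaths enter the comparison group as lost days.

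A reader might infer that an ineffective programme would appear to add 2 to 4 days at home. The documents do not support that figure: it rests on assumed stays, waits and uptake in an unmatched contrast. A reader might also infer that the primary result is biased. It is not by this route, because the stepped-wedge contrast uses site-period exposure.

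**Conclusion.** The gap is real, and it is one of specification: nothing aligns the start of follow-up with attendance, or requires comparators to be alive and at home when their counterparts attend. Where classes fall after day 0, the bias probably favours the programme, as it did in nearly all null scenarios. Its size is not derivable from the documents, which give no class dates, uptake, stay-length distribution or mortality. Varied assumptions give about 0 to 10 days. The low end comes from short repeated stays with four qualifying class dates. The high end comes from counting days after death at 10% mortality. Several ordinary scenarios reach the 2-day planned effect, so a difference of that size could not safely be read as benefit. The point concerns a sensitivity analysis only.

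**What to change.** For the as-treated analysis:

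1. Set the index date at the first class attended.
2. Give each matched comparison Veteran the same calendar index date, and judge comparison status on that date. Defining it by later events would bring the selection back.
3. Require both Veterans to be alive and at home on that date.
4. Measure matching covariates up to that date.
5. Count days not at home over the next 180 days.
6. State one rule for days after death, reconciling the description of the outcome with its formula. Also reconcile the two definitions of the outcome start.

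This is a cheap improvement. Attendance logs, pull dates, and admission and discharge dates are already among the planned data. The cost is reprogramming, somewhat fewer matched pairs, and some follow-up beyond the original window.
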